11.2 Criteria for study suspension/termination

11.2.1 Temporary study suspension

The study may be temporarily suspended in the following situations:

- Occurrence of one (1) SAE which is life-threatening or fatal and that is both unexpected and assessed as related to the use of emapalumab.
- At the IDMC own request as an outcome of their regular or ad hoc study data review.

Enrolment of any new patient will be suspended until further notice. Patients already enrolled in the study should continue receiving emapalumab per protocol unless decided otherwise by the Investigator.

In the case of study suspension, the IDMC will be promptly informed to allow for analysis of the data that were already generated and to provide recommendations which will also include further management of patients already enrolled in the study.

After evaluation of benefit/risk profile based on available data, the IDMC may recommend any of the following:

- Resume the study without any change in the conduct of the study.
- Resume the study with the amendment of the protocol to address any new safety concerns.
- Permanent study termination.

11.2.2 Study Termination for safety reasons

Termination of the study must be considered in the case of occurrence of two (2) deaths due to any reasons suggesting a reasonable possibility that the deaths are related to the use of emapalumab. This process will involve the IDMC, Sponsor and the Investigator. The management of patients already enrolled in the study will also be part of the IDMC recommendations.

11.2.3 Study Termination for efficacy reasons

The decision to terminate the study due to absence of a demonstrated benefit can be made by the Sponsor.

In case of study termination, the management of the patients already enrolled in the study will also be part of the IDMC recommendations.

12 STATISTICAL METHODS

12.1 Sample Size

In order to treat 4 patients for primary GF per cohort, it is expected to include between 15 to 40 patients to be monitored for primary or secondary GF per cohort. This is based on the assumption that between 10 and 30% of patients will present with a CXCL9 elevation above defined threshold when ANC is below 500 cells/ μ L during the monitoring period (Sobi AG internal data).

Considering a maximum of 3 sequential cohorts of 4 evaluable patients and 6 additional evaluable patients to the final cohort with determined dose and potential non-evaluable patients, it is expected that approximately a maximum of 250 patients will be included in the study to be monitored for GF.

Given the experience gained with emapalumab in other indications such as hemophagocytic lymphohistiocytosis (HLH) and macrophage activation syndrome (MAS), a robust PK/PD model has been developed, therefore 4 evaluable patients per cohort and a maximum of 3 cohorts are considered sufficient to confirm the PK/PD profile in post-HSCT patients and determine the appropriate dose regimen to pre-emptively treat patients at high risk of GF.

Assuming a similar rate of primary and secondary GF, a similar number of patients may optionally start treatment for secondary GF in each cohort. Additional patients may be treated for secondary GF in the final cohort with determined dose.

12.2 Interim analyses

Interim analyses (IAs) are planned when the last patient completes pre-emptive treatment for primary GF in a cohort (4 evaluable patients). Total IFN γ levels, CXCL9 levels and PK/PD data will be assessed for inclusion of additional dose cohorts. The benefit risk of emapalumab will be assessed by IDMC and sponsor before transitioning to the next dose regimen in cohort 2 or 3.

Once the appropriate dose regimen is determined in cohort 1, 2 or 3, a maximum of 6 additional evaluable patients may be added to the selected cohort. Additional IAs are planned when 7 and 10 evaluable patients have completed treatment with the selected dose, unless the study is stopped for futility or success. A final analysis with all data collected up to EoS will be included in a CSR.

IAs will be also performed after 1 and 2 years follow up calls and data collected up to 3 years follow up will be included in an addendum to the CSR.

Given that similar PK/PD profile of emapalumab is expected in patients treated to pre-empt primary and secondary GF, data obtained in the secondary GF patients may also be used.

The following guidance will be followed for inclusion of additional patients to the same cohort (once the appropriate dose has been selected) or to stop the study for futility or success.

After 4 evaluable patients have completed treatment for primary GF in a cohort with selected dose:

- 3 or more patients experienced GF, the study will be stopped for futility.
- 0 to 2 patients experienced GF, 3 additional patients may be added.

After 7 evaluable patients have completed treatment for primary GF:

- 5 or more patients experienced GF, the study will be stopped for futility.
 - 2 to 4 patients experienced GF, 3 additional patients may be added.
- 0 to 1 of the patients experienced GF, the study can be stopped for success.

12.3 Patients stratification

Patients will be stratified into two groups at screening (at least 40% malignant and 40% non-malignant) by means of an interactive response technology. Stratification will allow to explore the appropriate dose inhibiting IFN γ production in a similar number of patients presenting with malignant or non-malignant disease in each cohort.

12.4 Definition of study populations

The following analysis sets/populations will be used:

- All included population: This population will comprise all patients included in the study whether they are treated or not and will be used for presenting safety endpoints.
- All treated population: This population will comprise all patients who received at least one dose of investigational product and will be used for presenting efficacy endpoints.
- All evaluable population: This population will comprise all patients treated for primary GF who have:
 - No administration of any prohibited medication during treatment.
 - No premature treatment withdrawal for reasons other than safety or lack of efficacy.
 - Not more than 1 infusion missed.
 - No delay of treatment initiation (more than 36 hours from CXCL9 sample collection time with levels above threshold).

This population is the primary analysis population for determination of the appropriate dose regimen and to assess efficacy of emapalumab in pre-empting primary graft failure.

- Per protocol population: This population includes all evaluable patients without major protocol deviations. A major protocol deviation is here defined as a deviation that has been classified as major based on that it might influence the primary efficacy endpoint (pre-emption of GF). The per protocol population will be used to assess the appropriate dose regimen and efficacy of emapalumab in pre-empting primary GF.
- PK/PD population: This population will comprise all patients included in the study treated with emapalumab and with at least one post-dose PK sample. The PK/PD population will be used for presenting PK/PD endpoints.

12.5 Overall statistical and analytical plan

Full details of all statistical considerations and planned statistical analyses will be specified in the SAP, which will be finalized before the first interim analysis which takes place when the last patient in the first dose cohort completes his/her treatment period. This section contains an overview of the planned methods of analysis.

All analyses are considered exploratory. Data will be presented by emapalumab dose regimen, total emapalumab group and untreated group. The emapalumab groups will also be divided by treatment for primary graft failure (pGF) and secondary graft failure (sGF) and by malignant and non-malignant where applicable.

Continuous variables will be summarized using the number of patients, the mean, the standard deviation, the median, the minimum value, and the maximum value. Categorical variables will be summarized using frequency counts and percentages.

Statistical analysis will be performed using Statistical Analysis Software (SAS) software Version 4 or later (SAS Institute, Inc, Cary, North Carolina, United States).

12.5.1 Demographics and baseline characteristics

Demographic data and baseline characteristics will be presented using summary statistics.

12.5.2 Efficacy Data

Efficacy data will be summarized using descriptive statistics.

Point estimates for the efficacy endpoints will be presented together with the corresponding 95% confidence intervals (CI) in the appropriate dose cohort.

The relationship between selected covariates (e.g. biomarkers, baseline characteristics) and treatment response will be investigated.

The relationship between selected covariates and the risk of GF will be investigated in the untreated patients.

12.5.3 Safety Data

Safety data will be listed and summarized using descriptive statistics.

AEs will be coded and tabulated by body system, and by individual events within each body system. AEs will also be tabulated by severity and relationship to the study medication. Summaries will also be produced of SAEs and AEs leading to withdrawal of treatment.

For each clinical laboratory test, individual patient values will be listed and summarized, and change from pre-treatment baseline values calculated and summarized. Any values outside the standard reference range will be flagged. Summaries of marked abnormalities and shift tables or boxplots will be tabulated for each laboratory test.

In addition, other exploratory analyses of safety data, including summaries for different subsets of patients, may be conducted.

12.5.4 Pharmacokinetic and Pharmacodynamic Data

Pharmacokinetic and pharmacodynamic calculations

The serum concentration of free emapalumab will be measured as a function of time to determine the PK of emapalumab in this patient population. PK parameters will be calculated and used to support determination of the appropriate dose regimen of emapalumab.

NCA will be used to calculate the following PK parameters after each cohort: C_{max} (peak serum concentration), C_{trough} (concentration just before administration), C_{meantau} (mean concentration over a dosing interval) and AUC_{tau} (area under curve of a dosing interval). Other PK parameters may be calculated as appropriate.

In addition, at the end of the study individual emapalumab concentration-time data will be subject to population PK analysis using non-linear mixed effects modeling. The anticipated covariate effects of body weight and time-varying total IFN γ will be included in the model. Additional covariate effects might be investigated. A specific PK modeling analysis plan will be prepared.

An exploratory PK/PD analysis using non-linear mixed effects modeling will be conducted. The main PD biomarker investigated will be CXCL9. Additional PD biomarkers may also be evaluated. The anticipated covariate effect of time-varying total IFN γ will be included in the CXCL9 model. Additional covariate effects might be investigated.

The population PK and PK/PD analyses may be reported separately.

All PK and PD data will be summarized using descriptive statistics.

12.5.5 Exploratory analyses

The correlation between relevant biomarkers including CXCL9 levels and the risk of GF post allo HSCT will be evaluated in the untreated patients.

Specific exploratory analyses evaluating the impact of study endpoints when CXCL9 and other relevant biomarkers are measured with different analytical methods will be defined in a SAP.

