--	--

	
Exploratory endpoints
 
 • CXCL9 and other biomarkers relevant to the diagnostic test development measured with different analytical technologies.

STATISTICAL METHODOLOGY
	
All analyzes are considered exploratory. Efficacy and safety data will be presented by descriptive statistics.
 
Continuous variables will be summarized using the number of patients, the mean, the standard deviation, the median, the minimum value, and the maximum value. Categorical variables will be summarized using frequency counts and percentages.
 
For the appropriate dose cohort the point estimates for the efficacy endpoints will be presented together with the corresponding 95% CI.
 
The relationship between selected covariates (e.g. biomarkers, baseline characteristics) and treatment response will be investigated.
 
The correlation between CXCL9 levels and the risk of GF will be evaluated in the untreated patients.
 
The relationship between selected covariates and the risk of GF will be investigated in the untreated patients.

TABLE OF CONTENTS

SUMMARY OF CHANGES TO THE PREVIOUS PROTOCOL VERSION.....	5
PROTOCOL SYNOPSIS.....	7
LIST OF ABBREVIATIONS.....	22
1 BACKGROUND INFORMATION.....	25
1.1 Rationale for targeting Interferon gamma (IFN γ) in graft failure.....	25
1.1.1 Non-clinical evidence.....	25
1.1.2 Clinical evidence.....	26
1.1.3 Summary.....	27
1.2 Emapalumab.....	27
1.2.1 Description and Mode of Action.....	27
1.2.2 Preclinical Data.....	27
1.2.3 Clinical Data.....	28
2 OBJECTIVES.....	30
3 OVERALL STUDY DESIGN AND PLAN.....	30
3.1 Overall study design.....	30
3.2 Study design rationale.....	31
3.3 Transition between cohorts.....	32
3.4 Study periods.....	33
3.4.1 Screening Period.....	33
3.4.2 Allogeneic HSCT.....	33
3.4.3 Monitoring and extended monitoring periods.....	33
3.4.4 Treatment Period.....	34
3.4.5 Follow-Up Period.....	35
3.4.6 Unscheduled visit.....	37
3.4.7 Withdrawal visit.....	37
3.5 Study duration and study end.....	37
3.6 Study committees.....	37
3.6.1 Independent Data Monitoring Committee.....	37
3.6.2 Dose Decision Committee.....	37

4	STUDY POPULATION.....	38
4.1	Inclusion criteria.....	38
4.2	Exclusion criteria.....	38
4.3	Criteria for women of childbearing potential.....	39
4.3.1	Acceptable methods of contraception.....	39
5	INVESTIGATIONAL MEDICINAL PRODUCT	40
5.1	Description of Investigational Medicinal Product	40

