2 OBJECTIVES

The main objective of this proof of concept study is:

- To determine the appropriate emapalumab dose regimen neutralizing IFN γ activity to pre-empt graft failure post allogeneic HSCT in a population with various underlying diseases and at high risk of GF.

The following objectives will support the main objective:

- To describe the PK and PD profiles of emapalumab post allo-HSCT.
- To assess the efficacy of emapalumab to pre-empt GF post allo-HSCT.
- To assess the safety of emapalumab to pre-empt GF post allo-HSCT.
- To assess the immunogenicity of emapalumab post allo-HSCT.

Exploratory objectives will be:

- To evaluate further data on the correlation between relevant biomarkers including C-X-C motif chemokine ligand 9 (CXCL9) levels and the risk of GF post allo-HSCT in a population with various underlying diseases and at high risk of GF also in the context of development of a diagnostic test.

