3 OVERALL STUDY DESIGN AND PLAN

3.1 Overall study design

This study is an open-label, single arm, sequential dose cohorts, proof of concept phase 2 study and it enrolls children and adults receiving allogeneic HSCT who are at high risk of graft failure. Children less than 1 year old will be included only after the appropriate dose regimen has been determined in one of the three cohorts and safety assessed by an Independent Data Monitoring Committee (IDMC).

The study is comprised of the following study periods: screening (Day -21 to Day -8), allogeneic HSCT Day 0, monitoring period for primary GF (Day 1 up to Day 42), extended monitoring for secondary GF (up to Day 98), treatment period (up to 56 days) and follow-up period of 3 years after HSCT. The overall study design is shown in Table 1.

Patients presenting CXCL9 levels above a defined threshold and an ANC below 500 cells/ μ L will be eligible to receive emapalumab during the monitoring period (Day 1 to Day 42).

Patients presenting CXCL9 levels above thresholds and signs of secondary GF (i.e. donor chimerism drop of at least 10% for 2 consecutive measurements and/or absolute neutrophil count [ANC] below 500 cells/ μ L and/or thrombocytopenia below 30000/ μ L not explained by any other reason than potential graft rejection) during the extended monitoring period (up to Day 98) will also be eligible to receive emapalumab. Pre-emptive treatment for secondary GF is optional.

A maximum of 3 cohorts is foreseen to determine the appropriate dose to pre-emptively treat primary GF. Data will be analyzed after the last patient completes emapalumab treatment in each cohort. After each cohort, the Sponsor will decide whether to stop the study or to add an additional cohort with dosing regimen adaptation based on observed PK/PD profile and benefit risk profile.

Once the appropriate dose has been determined a maximum of 6 evaluable additional patients may be added to the corresponding cohort to explore the potential benefit of emapalumab in preventing primary GF.

Patients will be stratified at screening in order to include at least 40% malignant and 40% non-malignant (by means of an interactive response technology).

Table 1: Overall study design for cohort 1, 2 or 3

SCREENING	HSCT	MONITORING (Primary GF)	EXTENDED MONITORING (Secondary GF)	FOLLOW-UP (for emapalumab treated ² and non-emapalumab treated patients ³)
Day -21 to Day-8	Day 0	Day 1 to Day 42	Up to Day 98 ¹	3 years from HSCT

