3.4.3 Monitoring and extended monitoring periods

Assessments to be performed during the monitoring periods are presented in the schedule of assessment (Table 5a and Table 5b).

See Table 2 and Table 3 for details on the transition from monitoring to extended monitoring, treatment and follow up in case of ANC < 500/ μ L (Table 2) and \geq 500 cells/ μ L (Table 3) during the monitoring period.

CXCL9 measurements will be performed by means of a validated assay on a device provided to the sites by Sobi AG. The exact CXCL9 threshold for treatment initiation will be provided in the CXCL9 assay laboratory manual.

Monitoring period

The monitoring period will start from the day after the HSCT (day 1) and will last until ANC is \geq 500 cells/ μ L or maximum until monitoring day 42 \pm 1, whichever comes first. During the monitoring period, CXCL9 and ANC measurements will be performed daily from day 1 up to day 7, every other day starting from day 9 until day 21 and every 3 days (\pm 1) starting from day 24 until day 42.

- If CXCL9 is measured above threshold and ANC is below 500 cells/ μ L, patients will enter the treatment period.
- If CXCL9 is measured below threshold and ANC is below 500 cells/ μ L, patients will continue the monitoring period until day 42 \pm 1 or until a second HSCT is planned.
- As soon as the ANC will be \geq 500 cells/ μ L during the monitoring period, patients will move to the extended monitoring period for secondary GF (sGF).

Extended monitoring period

The extended monitoring period will start as soon as the ANC will be equal or above 500 cells/ μ L during the monitoring period and will last maximum 98 \pm 3 days.

During the extended monitoring, CXCL9 and ANC measurements will be performed weekly up to day 98 \pm 3 days. In case of signs of sGF outside of the weekly visits, the patient should attend for an unscheduled visit and the assessments foreseen in the extended monitoring period visit should be performed to assess eligibility for treatment.

- If CXCL9 is measured above threshold and there are signs of sGF (i.e. donor chimerism drop of at least 10% for 2 consecutive measurements and/or ANC below 500 cells/ μ L and/or thrombocytopenia below 30000/ μ L not explained by any other reason than potential graft rejection), patients may optionally enter the treatment period, if the investigator will consider pre-emptive treatment with emapalumab the best option for the patient.

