- If CXCL9 is measured below threshold, patients will continue the extended monitoring period until Day 98 \pm 3 days or until a second HSCT is planned.

Criteria not to start treatment during monitoring or extended monitoring

Patients presenting the following conditions at time of initiation of emapalumab treatment will not be eligible to receive emapalumab and will move to the phone-call follow-up period for non-emapalumab treated patients (see section 3.4.5).

- Uncontrolled infections (defined as clinically active infection regardless of treatment).
- Clinical manifestations of infections representing exclusion criteria (i.e. Atypical mycobacteria, Salmonella, Histoplasma capsulatum, Herpes zoster).
- Re-occurrence or progression of the underlying malignant disease based on medical judgment.
- GvHD.

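### The CXCL9–graft failure correlation is planned in untreated patients, a set selected on CXCL9 and ANC for primary GF; it supports GF frequency below threshold, not the overall relation

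*Combined protocol and SAP*

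**What the plan says.** The analysis set is stated twice. Section 12.5.5: "The correlation between relevant biomarkers including CXCL9 levels and the risk of GF post allo HSCT will be evaluated in the untreated patients". Synopsis, statistical methodology: "The correlation between CXCL9 levels and the risk of GF will be evaluated in the untreated patients".

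The exploratory objective in section 2 is wider. It concerns the correlation between biomarkers, including CXCL9 "levels and the risk of GF post allo-HSCT in a population with various underlying diseases and at high risk of GF", with a diagnostic test in view. Section 10.1 adds that untreated patients help to assess CXCL9 as a predictor of GF. Section 3.2 gives a narrower use: patients below threshold will show how often GF occurs there.

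Who is untreated follows from section 3.4.3:

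- Monitoring (primary GF): "If CXCL9 is measured above threshold and ANC is below 500", the patient enters the treatment period. Section 3.1 gives the same rule.
- Extended monitoring (secondary GF, sGF): CXCL9 above threshold and signs of sGF are both needed, and then "patients may optionally enter the treatment period, if the investigator will consider pre-emptive treatment with emapalumab the best option for the patient".
- Patients with uncontrolled or listed infections, relapse or progression, or GvHD when treatment would start "will not be eligible to receive emapalumab and will move to the phone-call follow-up period for non-emapalumab treated patients".

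Under sections 3.3 and 3.4.5, untreated patients also leave monitoring at a cohort hold, on prohibited medication or for a second HSCT. Their EoS visit is due within a week of the last monitoring day. Table 7 schedules GF recording up to EoS. The later calls cover survival, GvHD and a list of procedures and medications.

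**The concern.** A correlation between a predictor and an outcome should be estimated over the range of the predictor that the conclusion is about. Here the treatment rule for primary GF removes patients who have both high CXCL9 and low ANC. Section 1.1 says that GF is diagnosed on neutropenia, so ANC is close to the outcome. The set is thus selected on the predictor and on a variable tied to the outcome.

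The above-threshold patients who remain do not restore the missing range. Some had recovered ANC and so had already left primary-GF monitoring. Some were left untreated by investigator choice. Some were barred for infection, malignancy or GvHD. Each route may carry its own GF risk.

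What is at stake is the reading of CXCL9 as a marker. A weak correlation could be taken as evidence against it when the treatment rule produced the weakness.

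**Working it through.** **1. The plan's own figure.** No figure is stated for this correlation. The nearest is the 15 to 40 monitored patients per cohort in section 12.1, needed to treat 4 when 10–30% meet the primary-GF trigger: 4 / 0.30 = 13.3, rounded up to 14 (stated 15); 4 / 0.10 = 40 (stated 40). It reproduces closely. The 10–30% is the share with CXCL9 above threshold while ANC is below 500. It is not the share ever above threshold, so I derive no event counts from it.

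**2. Composition of the untreated set.**

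| CXCL9 | Other condition | Untreated because |
|---|---|---|
| Never above threshold | any | trigger not met |
| Above | ANC at or above 500, no signs of sGF | trigger not met |
| Above | signs of sGF | optional treatment not given |
| Above | infection, relapse/progression or GvHD | barred |
| Above | ANC below 500 in monitoring, not barred | not in the set: treated |

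The last row is the group on which a CXCL9–primary GF relation would mainly rest. For secondary GF the restriction is weaker, because treatment also needs signs of sGF and is optional.

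**3. Share of GFs below threshold.** Section 1.1.2 reports sensitivity of 90–100% in HLH patients (300 pg/mL) and 88.89% by day 3 in a second data set (274.5 pg/mL). The study threshold is in a laboratory manual, so carrying these over is an assumption. Share below threshold = 1 − sensitivity:

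- 1 − 1.00 = 0%
- 1 − 0.90 = 10%
- 1 − 0.8889 = 11.1%

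This is the share of GFs expected without treatment that would arise below threshold. It does not describe the whole untreated set.

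**4. Size of the distortion (illustration only).** A latent-normal model was simulated with PPV 86% and sensitivity 90–95% (HLH data, section 1.1.2) and 10–30% taken as the share above threshold.

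- Point-biserial correlation: 0.56–0.73 in all patients, 0.11–0.25 below threshold.
- The same, if a random 20% of above-threshold patients stayed untreated: 0.32–0.54.
- AUC: 0.983–0.998 in all patients, 0.938–0.989 below threshold.

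At 100% sensitivity there are no GFs below threshold, and no correlation can be estimated there.

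**5. Timing of the outcome.** Section 3.2 says that GF is usually confirmed between day 21 and day 42. EoS is due by the last monitoring day + 7. For a patient barred on day 3: 3 + 7 = day 10, which is 21 − 10 = 11 to 42 − 10 = 32 days too early. More generally, leaving both monitoring periods before day 14 (21 − 7) puts EoS before day 21, and leaving before day 35 (42 − 7) puts it before day 42. Section 12.5.6 plans observed data only and gives no rule for early leavers.

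**The case against.** The strongest reply is that treated patients must be left out, because treatment is meant to change GF. That stands, and I do not propose adding them.

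The set also holds above-threshold patients, and section 12.1 assumes similar rates of primary and secondary GF. So a reader might infer from the 0–11% that few GFs will be available in the whole untreated set. The documents do not support that: GFs among barred patients, those not given optional treatment and those with recovered ANC count too. Their number cannot be derived.

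GF after EoS is not wholly invisible. The calls record further transplants, stem cell boosts, DLI, transfusions and survival, and an unscheduled visit may record GF. Section 10.1 says that a second transplant is the only treatment once GF is confirmed. These are useful markers, but indirect or optional.

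The statistic is not named, and the illustration shows AUC falling much less than a correlation coefficient. That stands against any fixed size for the distortion. It does not make the set representative.

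A reader might also infer that the sponsor plans to estimate PPV, sensitivity or a cut-off from untreated patients. No text says so. The objective speaks only of further data on a correlation.

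Finally, section 12.5 leaves full details to a SAP, and the supplied text holds only the overview in section 12. The specific deferral in section 12.5.5 concerns measurement by different analytical methods; the analysis set itself is already fixed.

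**Conclusion.** The concern holds in this limited form. For primary GF, the untreated set is selected on CXCL9 and ANC. A correlation from it describes that set and does not estimate the relation in the high-risk population of section 2. The set does support the use in section 3.2, the GF frequency below threshold, if early exits are handled. For secondary GF the restriction is weaker.

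The one figure that can be given is that about 0–11% of GFs expected without treatment fall below threshold. It rests on the reported sensitivities carrying over to an unstated study threshold.

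Two wider readings fail. All analyses are exploratory, and nothing in dose selection, the main efficacy endpoint or the stopping guidance depends on this one. The plan in section 12.5.2, "The relationship between selected covariates and the risk of GF will be investigated in the untreated patients", shares the set but is not aimed at the variable that defines it, and needs no change. The point should be fixed because the objective looks towards a diagnostic test and the change is cheap.

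**What to change.** In section 12.5.5 and the synopsis:

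1. Make the main untreated-patient analysis the cumulative incidence of GF, with 95% CI, in patients with no CXCL9 value above threshold so far. Count a second HSCT given for GF as a GF event. Treat death without GF as a competing event. Censor those who leave for other reasons (cohort hold, prohibited medication) at their last GF assessment, and show the numbers leaving by reason. Say how a first value above threshold ends follow-up in this analysis; plain censoring there would be informative. Do not restrict to patients with complete monitoring: those leaving for a second HSCT are likely to be the GFs that CXCL9 missed, and dropping them would flatter the marker. A simple binomial proportion would count early leavers as free of GF. As a sensitivity analysis, count a second HSCT reported at the calls as probable GF.
2. Tabulate untreated above-threshold patients separately by reason untreated, with GF status and day of EoS.
3. State that any CXCL9–GF correlation in untreated patients is descriptive of this selected set, and is not an estimate of the overall relation or of PPV, sensitivity or a cut-off for primary GF.

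Cost: protocol and SAP wording, with no change to visits or treatment rules. The documents do not say whether the reason for not treating is captured; if it is not, one eCRF item is needed. The downside is a narrower claim about CXCL9 from this study.
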